Statistical analysis plan for Safer Births Bundle of Care, phase II

Version: 1.0 Date: October 28, 2025

This Statistical Analysis Plan (SAP) describes analytical approaches for the assessment of intervention effects on perinatal and maternal (clinical) outcomes of the Safer Births Bundle of Care (SBBC) project, phase II (registered as ISRCTN92381311), and for exploring promotors and inhibitors for change. It was finalized before completion of the data, but after some preliminary, descriptive analyses on partial data, including observed rates of outcome over time and assessment of missingness.

1 Introduction

SBBC phase II is a quality improvement study, implemented in 142 facilities in five regions in Tanzania. These facilities comprise all CEmONC (Comprehensive Emergency Obstetrics and Newborn Care) facilities in these five regions. Among the facilities, 30 took part in SBBC phase I and 112 facilities are new. As such, SBBC phase II represents an upscaling but also introduced new elements vis a vis SBBC phase I, see the protocol at https://www.isrctn.com/ISRCTN92381311 for details.

Identification of eligible facilities and central preparations started in December 2023. From January 2024 preparations for the implementation took place at the individual facilities, and the intervention started April-June 2024.

2 Data

Baseline data from 2023 and the first months of 2024 were collected retrospectively from prospectively registered births in hospital books for the 112 new facilities. For the 30 facilities continuing from SBBC phase I, baseline data from this period were gathered prospectively via the data system set up for SBBC phase I. From March 2024, designated data collectors visited all facilities regularly i.e. at least biweekly, registering data on newly recorded births from hospital books.

Recorded information from hospital books included outcomes and clinical variables (mother's age and parity, child's gender, birth weight, number of fetuses, etc.) related to the child and the mother. Every child and every birth have a unique ID number. Unfortunately, repeated births by the same mother cannot be identified.

Prospective collection of additional clinical data (source of admission, fetal heart rate, device use, etc.) was done separately starting June 2024 (fully operable from August 2024), i.e., only in the intervention period, and not linked to the individual births. Data about training practices at each facility were recorded by a separate digital system (LIFT) related to the training devices. Other facility related information (staff density) were collected from hospital management. Readiness data at baseline were collected using a standardized WHO form (Juma et al, 2024).

Data collection on all facilities will be running until end 2025. More details about the data gathering systems are given in the protocol and the data management plan at https://www.isrctn.com/ISRCTN92381311. Descriptions of outcome variables and covariates relevant for the analyses described in the analysis plan are given below.

2.1 Outcomes

Two primary outcomes were listed in the protocol, and are defined as:

- Perinatal death defined as intrapartum stillbirth (ISB) or newborn death within the first 24 hours of life.
- Maternal death within seven days postpartum.

Unfortunately, death within 24 hours is not directly available in the collected data from hospital books, apart from for newborns admitted to NICU. For all others, we have status at discharge and date (but not time of day) of discharge. We will define "early newborn death" as discharged as dead within (i.e., including) the date of birth plus one day. Which means that, depending on the time of day of the birth, death may have occurred at most <48 hours after birth.

Similarly, seven days maternal mortality will be defined as being dead at discharge if date of discharge for the mother is at most seven days after the date of delivery. (If date of discharge is missing for mother, we will impute it using date of discharge for child.)

For the baseline data from SBBC-I facilities, we do have the 24-hour newborn deaths and the sevendays maternal deaths directly available. However, to make the rates comparable, we will apply the same definitions to these data as well.

For perinatal death, newborns that are referred out during the first 24 hours will be regarded as having unknown outcome. Antepartum/macerated stillbirths (ASB) will be excluded from the sample. For maternal death, mothers referred out before seven days will be considered to have unknown outcome. ASB will be included and used as an adjustment variable when considering maternal outcome.

The following secondary outcomes were defined:

- 24-hour newborn death.
- Intrapartum stillbirth (ISB).
- 7-days perinatal death (including ISB).

The 24-hour newborn deaths will be redefined as "early newborn deaths" as above. Seven-days newborn deaths will be assessed using status at discharge and date of discharge as for maternal outcome.

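### The newborn death window runs by calendar date to the day after birth, but the referral-out rule still stops at 24 hours, so referrals between the two limits have no clear outcome status

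*SAP*

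**What the plan says.** All the relevant rules for the co-primary perinatal outcome stand in SAP section 2.1.

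- **Outcome as listed in the protocol:** "Perinatal death defined as intrapartum stillbirth (ISB) or newborn death within the first 24 hours of life".
- **Limit of the data:** 24-hour death is directly available for newborns admitted to NICU. "For all others, we have status at discharge and date (but not time of day) of discharge". It is also directly available in the baseline data of the SBBC-I facilities, but the SAP applies the date-based definition there too, for comparability.
- **Operational death window:** early newborn death means "discharged as dead within (i.e., including) the date of birth plus one day". The SAP notes the consequence: "depending on the time of day of the birth, death may have occurred at most <48 hours after birth".
- **Referral-out rule:** "For perinatal death, newborns that are referred out during the first 24 hours will be regarded as having unknown outcome".
- **Maternal counterpart:** "mothers referred out before seven days will be considered to have unknown outcome", while a maternal death counts when discharge is up to and including seven days after delivery.

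The last sentences of section 2.1 carry the date-based definition over to the secondary 24-hour death outcome. No sentence carries it over to the referral rule. Section 6 then builds the worst case for perinatal death by recoding certain missing outcomes as fatal, and referred-out newborns are the first group listed.

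**The concern.** An outcome and the rule that declares it unknown should cover the same follow-up window. Here the outcome was moved to calendar dates and the rule was not. This has two consequences.

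First, the rule cannot be carried out from dates. A referral dated the day after birth may lie before or after 24 hours. Two analysts could reasonably classify it differently, and the SAP does not choose between them.

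Second, on the literal reading, a newborn that left alive after 24 hours but within the death window is neither dead at discharge nor unknown. By default it is a non-event, although the facility cannot see what happened in the remaining hours. Because it is not missing, the worst-case analysis does not reach it. Yet section 6 itself treats referred-out newborns as a group whose unknown outcomes might be fatal.

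At stake are the reproducibility of a co-primary outcome and the completeness of its worst-case bound.

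**Working it through.** **1. Reproduce the SAP's own figure.** Let a birth occur u hours after midnight, 0 ≤ u < 24. The death window closes at the midnight that ends the next day, so its length is 48 − u hours. This runs from just over 24 up to 48 hours, which agrees with the limit of under 48 hours in section 2.1.

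**2. Part of the window the referral rule leaves open.** The rule covers the first 24 hours, so the gap is (48 − u) − 24 = 24 − u hours. Assuming births spread evenly over the day (mean u = 12):

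- mean window = 48 − 12 = 36 hours
- mean gap = 24 − 12 = 12 hours
- share uncovered = 12/36 = one third
- share of the day after birth that lies beyond 24 hours = 12/24 = one half, so the date alone does not settle a referral on that day.

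**3. What each reading of the rule does.**

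| Reading | Referral dated day of birth | Referral dated next day | Gap |
|---|---|---|---|
| Literal 24 hours (needs clock time) | unknown | unknown if within 24 h, otherwise non-event | mean 12 h |
| Same-day referrals only | unknown | non-event | mean 24 h (whole next day) |
| Through date of birth plus one day | unknown | unknown | 0 h |

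**4. Effect on the available-case rate.** The SAP gives no referral-out rates, so the affected share r is assumed. If 1% of newborns are referred out and 20–33% of those leave in the uncovered part, r = 0.01 × 0.20 = 0.20% to 0.01 × 0.33 = 0.33% of births. With D deaths among N births, counting these newborns as non-events gives D/N, and treating them as unknown gives D/[N(1 − r)]. The ratio is 1/(1 − r), which is 1.0020 to 1.0033, or about 0.2–0.3% relative. With r from 0.1% to 1%, the change is about 0.1% to 1%.

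**5. Effect on the relative risk.** With r₀ at baseline and r₁ in the intervention period, the relative risk is multiplied by (1 − r₀)/(1 − r₁). Equal shares give exactly 1. With r₀ = 0.20% and r₁ = 0.33% the factor is 0.9980/0.9967 = 1.0013.

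**6. Effect on the sensitivity bounds.** The best case sets all missing outcomes to non-fatal, so compared with the literal reading it does not move. The worst case sets missing referred-out newborns to fatal, so it rises by r, here 0.20 to 0.33 percentage points. Against an assumed event rate of 1% to 1.5%, that is between 0.20/1.5 = 13% and 0.33/1.0 = 33% of the event rate. The bound is therefore far more sensitive to the rule than the main estimate is.

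**The case against.** The strongest reply is that the rule is ambiguous rather than wrong. If 24 hours cannot be found from dates, no analyst can single out newborns referred after 24 hours and code them as survivors. A calendar rule will have to be used, and the natural choice is the one already adopted for deaths, under which the problem vanishes. That is fair. A reader might infer that the SAP does count late referrals as survivors. It does not say so: this follows from the literal wording only, and the intended practice is not stated. What stands is that the text does not choose, and that a same-day reading would enlarge the gap.

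A second reply is that, for the protocol's 24-hour outcome, a newborn referred out alive after 24 hours is a known non-event. That is correct. The mismatch exists only relative to the date-based proxy, but that proxy is what will be analysed.

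A third is that it is too broad to say only dates exist. The SAP excepts NICU admissions and SBBC-I baseline data, and its date-only statement concerns discharge; how referral-out is timed is not described.

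A reader might also infer a sizeable bias in the relative risk, on the ground that referral patterns are expected to change. Section 3.2 says only that such changes may play a role, in a sentence about comparisons between regions, facility levels and SBBC-I status, and it expects no change in the population. Nor do the documents support a figure for deaths missed. It would need an assumed mortality after late referral, and the change of rule would not recover those deaths, since it only makes the outcomes unknown.

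The maternal difference concerns only mothers referred out on day 7 itself. It is a minor edge.

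**Conclusion.** The inconsistency is real and lies within section 2.1: deaths are defined by date, referral-out by hours, and the second cannot be derived where only dates are recorded. On the literal reading, an average of 12 of 36 hours of the death window is uncovered, assuming births spread evenly over the day.

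The size of the effect is unknown because the SAP gives no referral-out rates. On the assumed 0.2–0.3% of births, the available-case rate moves by a similar relative amount and the relative risk hardly at all if the periods are alike. The documents do not support a claim that the main efficacy estimate is materially biased. What is affected is which newborns enter the missing set, and through it the worst-case bound, together with the reproducibility of a co-primary outcome. It should be corrected for those reasons.

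**What to change.** In section 2.1, state that the newborn outcome is unknown when the child is referred out alive on or before date of birth plus one day. Apply this in both periods and to all data sources, including NICU admissions and SBBC-I baseline data. For consistency, treat the 7-day outcomes, newborn and maternal, as unknown when the person is referred out alive on or before day 7.

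This is a sentence or two and uses the same date arithmetic as the death definitions. The cost is slightly more unknown outcomes and a somewhat wider best/worst-case range, which then covers the whole of the death window.

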2.2 Covariates

In Table 1 an overview of covariates considered relevant for the clinical outcomes are listed. These variables are considered to be the most relevant prognostic factors, without too serious reliability and missingness issues.

Table 1: Overview of covariates relevant to include in the modelling

Covariate	Available period (baseline/intervention)	Available at level (individual/facility)	Fixed or time- varying	Details	Comment
Child	, ,	, , , , , ,	, 0		
Birth weight	Both	Individual	Time-varying	Grams	
Sex	Both	Individual	Time-varying	Male, female, ambiguous, or unknown	Ambiguous and unknown regarded as missing
Mother/pregnancy					
Age	Both	Individual	Time-varying	Years	
Parity	Both	Individual	Time-varying	Mother's number of previous births	
Multiples	Both	Individual	Time-varying	Number of fetuses	Dichotomize into one or more than one
ASB	Both	Individual	Time-varying		Adjustment variable for maternal outcome; ASB excluded for perinatal/newborn outcomes
Source of admission ¹	Intervention	Facility	Time-varying	Home, referral, or unknown → monthly proportions of referral-ins (unknown disregarded)	
Fetal heart rate (FHR) at admission ¹	Intervention	Facility	Time-varying	Heard/present, not heard/not present, or not measured/unknown → monthly proportions of not heard/present (not measured/unknown disregarded)	
Term/preterm ¹	Intervention	Facility	Time-varying	Term or preterm → monthly proportions of preterm	
Use of Moyo ¹	Intervention	Facility	Time-varying	Yes, no, or unknown → monthly proportion of births where Moyo used	
Facility					
Region	Both	Facility	Fixed	Five regions	

Level of health	Both	Facility	Fixed	Health center, district hospital,	
facility				or regional referral hospital	
Staff density	Both	Facility	Fixed	Number of healthcare workers at the	Assume representative
				facility at the start of the intervention	for the whole study
				period, divided by the average number	period
				of births per month at the facility	
				during the intervention period,	
				multiplied by 100	
Readiness level	Baseline	Facility	Fixed	0-100	
Training data – Team	Intervention	Facility	Time-varying	Monthly amount of team scenario	
training				training (average 5 persons involved)	
				divided by number of staff. Assume	
				effect lagged by one month. Also	
				consider cumulative amount of	
				training.	
Training data –	Intervention	Facility	Time-varying	Monthly amount of individual skill	
Individual skill				training divided by number of staff.	
training				Assume lagged effect (one month).	
				Also consider cumulative amount of	
				training.	
Mentorship visits	Intervention	Facility	Time-varying	Number of mentorship visits. Assume	Number of mentors
				lagged effect (one month). Also	larger for larger units
				consider cumulative number of visits.	for the planned visits,
					but not for the
					unplanned ones.

¹⁾ These variables were collected on a separate form for each birth during most of the intervention period (starting June 2024) but not linked to the other information about the individual births, thus can only be used as facility level variables.

3 (Main) Analysis

3.1 Descriptive

Basic tabular summaries of outcomes, clinical variables, and process variables will be presented, stratified by the two intervention periods (baseline, intervention). These tables will be made separately for facilities that was part of SBCC phase I and the new hospitals. Further, tables stratified by region and hospital level will be made.

3.2 Estimation of overall efficacy

Logistic regression will be used to assess the overall efficacy of the intervention, including data from all 142 facilities. We anticipate varying intervention effects per region and per facility level and depending on whether the facility was part of SBBC phase I or not, and possibly also varying intervention effects between combinations of these factors. Further, we anticipate time-varying intervention effects as well as clustering on two levels, birth (for multiples) and facility.

Thus, the full model will be a mixed-effects logistic regression model, incorporating the following:

Fixed effects:

- a) Time-varying intervention effects modelled using a continuous variable representing time since intervention start (set to zero for all baseline observations). To capture potential nonlinear effects, time will be modelled using splines. The spline-transformed time variable, f(t), will be interacted with an indicator for intervention status (intervention vs. baseline), i.e., I(intervention).
- b) Region-specific treatment effects, modeled through an interaction between region (five regions) and the intervention-by-time spline term, $I(\text{intervention}) \cdot f(t)$.
- c) Facility level-specific treatment effects, modeled through an interaction between facility level (three levels) and $I(\text{intervention}) \cdot f(t)$.
- d) Differing treatment effects between facilities that were part of SBBC phase I and those new in SBBC phase II, through interaction between SBBC-I (yes/no) and I(intervention) $\cdot f(t)$.
- e) All higher level interactions between region, facility level, SBBC-I, and $I(\text{intervention}) \cdot f(t)$.

Random effects:

f) Random effects (random intercepts and random intervention effects) for facilities and for births nested within facilities.

In Stata syntax, the full regression model looks like this:

```
i.region i.facility_level i.sbbc_phase1 i.intervention ///
i.intervention#c.s_time ///
i.region#i.intervention#c.s_time ///
i.facility_level#i.intervention#c.s_time ///
i.sbbc_phase1#i.intervention#c.s_time ///
i.region#i.facility_level#i.intervention#c.s_time ///
```

```
i.region#i.sbbc_phase1#i.intervention#c.s_time ///
i.facility_level#i.sbbc_phase1#i.intervention#c.s_time ///
i.region#i.facility_level#i.sbbc_phase1#i.intervention#c.s_time ///
|| facility_id: i.intervention i.intervention#c.s_time ///
|| birth_id: i.intervention i.intervention#c.s_time ///
, covariance(unstructured)
```

In the (likely) case of convergence problems, the model will be reduced in the following order:

- 1. Reducing complexity in the random effects.
- 2. Reducing complexity in the fixed effects by removing higher order interactions.
- 3. Reducing complexity in the fixed effects by reducing the degrees of freedom for the splines of time, ultimately assuming linear effect of time.
- 4. After each reduction in fixed effects, try in the random effects again.

Regarding 1: Experience from SBBC phase I was that the clustering on birth level (for multiples) was difficult to account for without convergence issues. If the same problem is encountered here and not resolved by removing random intervention effects at two levels, we will resort to the same solution as used in phase I, i.e., including only one of the babies in births with multiples.

Once a model has been identified that converges successfully and shows no signs of numerical instability, we will proceed to reducing the fixed effects structure by optimizing Akaike's Information Criterion (AIC). Specifically, any parameter whose removal results in a reduction of the AIC by at least 2 will be excluded from the model. If possible, random effects will be reintroduced.

In SBBC-I, FHR at admission was by far the most important individual-level adjustment variable for perinatal deaths, and for maternal deaths, FHR at admission and ASB were most important. Referral-in (yes/no) was also of some importance. FHR at admission and referral-in are only available in the intervention period here and only on facility level (FHR also in a less informative variable than in SBBC-I), and this is also the case with preterm (yes/no). Thus, in addition to ASB (for maternal outcome), we will in the current analyses have to suffice with adjusting for birth weight (categorical including "missing" as a category), mother's age (non-linear effect), and multiples (yes/no), which all were found to have some adjustment effect in SBBC-I. Since we do not expect changes in the population during the study period, these adjustments will be mostly relevant for comparisons between regions, facility levels, and SBBC-I (yes/no), where changes in referral patterns among the participating facilities during the intervention may play a role.

The overall effect of intervention will be presented as the marginal relative risk (RR) at 1.5 years after start intervention, obtained using g-computation (Snowden et al, 2011). Maximum likelihood estimation will be used for model fitting, the final model will be fitted using restricted maximum likelihood.

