Adjustments will be made for monthly rates of referrals-in, births with not heard/detected FHR, and preterm births for each facility. Since these, as well as data regarding use of Moyo and NeoBeat, are only available for a substantial proportion of births from August 2024 and onwards, adjusted results and results for the latter predictor variables will be presented for the period August 2024 to December 2025. Unadjusted results, and results adjusted for BW, mother's age, and multiples, will be presented for the whole intervention period whenever possible.

In these analyses, the 30 SBBC-I facilities and the 122 new facilities will be analyzed separately.

4 Reporting and multiplicity considerations

Due to the non-randomized pre-post design of the study no causal claims will be made based on the estimated effects/associations.

All estimates will be presented with 95% confidence intervals (CI) and corresponding p-values from significance tests. For the estimates of overall efficacy for the two co-primary outcomes, p-values <0.025 will be considered statistically significant. All other p-values will be interpreted as exploratory.

If a confidence interval goes beyond the region of possible values for the parameter, we will report the interval truncated to possible values.

5 Graphical displays of results

Results from the main analyses will be supplemented with prediction plots based on the final models.

Furthermore, to accompany the CUSUM plots and illustrate the impact of the intervention over time, variable life adjusted displays (VLAD) will be made (Lovegrove, 1997). These plots will be made by aggregating the difference between the estimated conditional probability for fatal outcome based on a model estimated from baseline data, and the observed outcome, and can thus be interpreted in terms of estimated numbers of lives saved. The same logistic regression models as used for the CUSUM plots described in Section 3.3 will be used to estimate the probability of fatal outcome under baseline conditions.

For the promotor/inhibitor analyses, estimated marginal rates will be presented over time for each considered factor, based on the Poisson regression models.

6 Missing data and sensitivity analyses

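### The primary model has no calendar-time or season term, so a secular trend passes fully, and season partly, into the RR at 1.5 years; the net direction of bias is unknown

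*SAP*

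**What the plan says.** SAP Section 3.2 defines the time variable as "time since intervention start (set to zero for all baseline observations"). The main effects in the Stata syntax are "i.region i.facility_level i.sbbc_phase1 i.intervention". The only time term is "i.intervention#c.s_time", together with its interactions with region, facility level and SBBC-I. The adjustment covariates are birth weight, "mother's age (non-linear effect), and multiples (yes/no"), plus antepartum stillbirth for the maternal outcome. The overall effect is the "marginal relative risk (RR) at 1.5 years after start intervention", obtained by g-computation.

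On dates, Section 1 says that "the intervention started April-June 2024". Section 2 places the start of the baseline data in 2023 and the end of data collection at the end of 2025.

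Section 4 tests each co-primary estimate at 0.025 and states that "no causal claims will be made based on the estimated effects/associations". Section 5 says that the variable life adjusted display (VLAD) "can thus be interpreted in terms of estimated numbers of lives saved".

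**The concern.** No listed effect and no line of the syntax represents calendar time, a pre-intervention slope, month or season, and the covariates do not supply one. The model therefore takes baseline risk as constant from January 2023 to the start of the intervention and projects that constant to late 2025. Whatever else moved mortality over that time is absorbed by the intervention-by-time term.

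In an uncontrolled pre-post study, secular trend and season are the obvious rival explanations. The plan holds 15-17 months of dated baseline births and makes no use of their timing. Section 3.2 says that the population is not expected to change, but that is not an assumption about mortality trend or season. The Section 6 sensitivity analyses concern missing outcomes only. The Section 7 trend plots cover antepartum stillbirth and deaths on days 2-7, and its baseline comparison concerns data quality. None of these adjusts the primary RR. At stake is whether a formally significant result for either co-primary outcome could arise, or be hidden, without any intervention effect.

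**Working it through.** The SAP states no bias, trend or power figure on this point, so there is none to reproduce.

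**Inputs from the SAP.** Baseline runs from January 2023 to a start in April-June 2024, so B = 15-17 months. The evaluation point is start + 18 months, about October-December 2025. The threshold is 0.025.

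**Assumptions (not in the SAP).** Annual trend; seasonal amplitude ±10% on the odds; baseline risk 1.5%; 5,000-20,000 births per month in total; starts split equally over 1 April, 1 May and 1 June 2024; a 20% reporting step; random effects ignored.

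**Trend.** The gap from the mean baseline birth to the evaluation point is B/2 + 18 = 25.5-26.5 months, or 2.13-2.21 years. With no intervention effect and an annual ratio r, the model returns about r^gap:

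| Assumed r per year | RR with no effect |
|---|---|
| 0.98 | 0.98^2.13 to 0.98^2.21 = 0.96 |
| 0.96 | 0.96^2.13 to 0.96^2.21 = 0.92 to 0.91 |
| 0.94 | 0.94^2.13 to 0.94^2.21 = 0.88 to 0.87 |
| 1.05 | 1.05^2.16 = 1.11 |

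The fixed-effect core (intercept, intervention, intervention × f(t), t = 0 in baseline) was also fitted to noise-free expected monthly counts. The results are the same, and nearly identical for a linear term and for restricted cubic splines with 2-4 df. The choice of spline does not remove the bias. A true OR of 0.80 with a 5% yearly decline is returned as 0.80 × 0.95^2.16 = 0.716.

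**Chance of p<0.025 with no effect.** At r = 0.95 the log shift is 2.16 × ln 0.95 = -0.111. At 20,000 births per month the SE is 0.032, so the shift is about 3.5 SE against a critical value of 2.24, giving a probability of 0.89. At 10,000 and 5,000 births per month it is 0.58 and 0.30. Facility-level variance would lower these figures.

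**Season.** With ±10% amplitude and no effect, the estimate at 1.5 years ranges over 0.92-1.08 with 3-4 spline df and about 0.96-1.05 with a linear term. The sign depends on the peak month. Adding one annual sine/cosine pair returns 1.00.

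**Reporting change.** Section 7 expects substantial under-reporting in the retrospective baseline of the new facilities, which ends in February 2024. Suppose recorded mortality rises by 20% in March 2024 with no effect and no trend. With 14 retrospective and 2 prospective months in a 16-month baseline, the mean baseline level is (14 × 1 + 2 × 1.2)/16 = 1.025. The model then returns 1.2/1.025 = 1.17 for facilities with that step.

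**After the change.** With a linear calendar term the estimate is 1.00 for every trend tried (r = 0.85 to 1.05). In the reporting-step scenario the calendar term alone gives 0.96, because the step distorts the fitted slope; with a data-source step term it gives 1.00. The SE of the log OR rises from 0.032 to 0.087, and 0.087/0.032 = 2.7. The ratio is up to about 3.2 with a linear time term.

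**The case against.** The strongest reply has five parts, and much of it stands.

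- **Coding.** Setting time to zero in baseline is ordinary coding for an intervention-by-time term and would be correct beside a calendar term. This stands: the gap is the missing term, not the zero.
- **Estimand.** An RR at 1.5 years is legitimate when effects are expected to vary over time. Section 7 already plans marginal RRs at other time points, and Section 5 adds prediction plots. This stands too, but those quantities come from the same model and share its flat baseline.
- **VLAD.** A reader might infer that the lives-saved figure is the tested contrast. It is not. The VLAD sums expected minus observed outcomes over the intervention period, using the baseline-only logistic models of Section 3.3. The two share the assumption of a constant baseline risk, and the wording sits badly with Section 4, but that is a matter of labelling.
- **Direction.** A reader might infer that the plan is biased in favour of the intervention, or that season is counted in full as effect. The SAP supports neither. It gives no trend and no seasonal size, season passes only in part and either way, and the expected under-reporting pushes the RR upward.
- **Acknowledged limits.** The SAP disclaims causal claims because of the design. That softens interpretation, but it changes neither the estimator nor the test at 0.025.

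**Conclusion.** The gap is real and should be fixed, but it does not invalidate the plan. The primary model cannot separate secular trend from intervention effect, and separates season only in part. The trend bias is about r^2.2 for an annual ratio r: 0.96, 0.92 and 0.87 for assumed declines of 2%, 4% and 6% per year, and above 1 for a rising trend. An assumed ±10% season moves the RR within about 0.92-1.08. An assumed 20% improvement in reporting gives about 1.17 in the facilities affected.

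The structural statement rests on the SAP's own model and dates. The sizes rest on the assumptions listed, so the net direction of bias is not established. The steep loss of precision is the reason to place the trend-adjusted model beside the primary RR rather than in its place.

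**What to change.** 1. Add a 12-month sine/cosine pair for calendar month to the main model in Section 3.2, and exempt it from the AIC reduction. Cost: two parameters.
2. Pre-specify in Section 6, beside the primary RR, a sensitivity analysis using the same model with a linear calendar-time term across baseline and intervention. Include a step term for retrospective versus prospective data collection in the new facilities, and show SBBC-I and new facilities separately. State that its SE is about 2.7 times larger, because a slope from 15-17 months is extrapolated 1.5 years. At the assumed 20,000 births per month, a 95% CI around RR 1.00 would widen from exp(±1.96 × 0.032) = 0.94-1.06 to exp(±1.96 × 0.087) = 0.84-1.19. The analysis shows how far the result depends on a flat baseline; it will seldom be decisive alone.
3. Optionally, add the RR averaged over months 7-18 to the supplementary RRs in Section 7, keeping the 1.5-year RR as primary. Covering one full year, it narrows the assumed seasonal range to 0.98-1.02 without a harmonic term. It is a different estimand that mixes in earlier effects.
4. In Section 5, describe the VLAD as expected minus observed deaths relative to baseline risk, consistent with Section 4. Cost: wording only.

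No new data are needed. The terms should be fixed before the data are complete, because a trend model added later would look post hoc.
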